11.43 Response Criteria

11.431 All target lesions and target lymph nodes followed by CT/MRI/PET-CT/ /physical examination must be measured on re-evaluation at evaluation times specified in Section 11.1. Specifically, a change in objective status to either a PR or CR cannot be done without re-measuring target lesions and target lymph nodes.

Note: Non-target lesions and non-target lymph nodes should be evaluated at each assessment, especially in the case of first response or confirmation of response. In selected circumstances, certain non-target organs may be evaluated less frequently. For example, bone scans may need to be repeated only when complete response is identified in target disease or when progression in bone is suspected.

11.432 Evaluation of Target Lesions

- Complete Response (CR): All of the following must be true:
 - a. Disappearance of all target lesions.
 - b. Each target lymph node must have reduction in short axis to <1.0 cm.
- Partial Response (PR): At least a 30% decrease in PBSD (sum of the longest diameter for all target lesions plus the sum of the short axis of all the target lymph nodes at current evaluation) taking as reference the BSD (see Section 11.41).
- Progression (PD): At least one of the following must be true:
 - a. At least one new malignant lesion, which also includes any lymph node that was normal at baseline (< 1.0 cm short axis) and increased to ≥ 1.0 cm short axis during follow-up.
 - b. At least a 20% increase in PBSD (sum of the longest diameter for all target lesions plus the sum of the short axis of all the target lymph nodes at current evaluation) taking as reference the MSD (Section 11.41). In addition, the PBSD must also demonstrate an absolute increase of at least 0.5 cm from the MSD.
 - c. See Section 11.32 for details in regards to the requirements for PD via FDG-PET imaging.
- Stable Disease (SD): Neither sufficient shrinkage to qualify for PR, nor sufficient increase to qualify for PD taking as reference the MSD.

11.433 Evaluation of Non-Target Lesions & Non-target Lymph Nodes

- Complete Response (CR): All of the following must be true:
 - a. Disappearance of all non-target lesions.
 - b. Each non-target lymph node must have a reduction in short axis to <1.0 cm.

- Non-CR/Non-PD: Persistence of one or more non-target lesions or non-target lymph nodes.

- Progression (PD): At least one of the following must be true:
 - a. At least one new malignant lesion, which also includes any lymph node that was normal at baseline (< 1.0 cm short axis) and increased to ≥ 1.0 cm short axis during follow-up.
 - b. Unequivocal progression of existing non-target lesions and non-target lymph nodes. (NOTE: Unequivocal progression should not normally trump target lesion and target lymph node status. It must be representative of overall disease status change.)
 - c. See Section 11.32 for details in regards to the requirements for PD via FDG-PET imaging.

11.44 Overall Objective Status

The overall objective status for an evaluation is determined by combining the patient's status on target lesions, target lymph nodes, non-target lesions, non-target lymph nodes, and new disease as defined in the following tables:

For Patients with Measurable Disease

Target Lesions & Target Lymph Nodes	Non-Target Lesions & Non-Target Lymph Nodes	New Sites of Disease	Overall Objective Status
CR	CR	No	CR
CR	Non-CR/Non-PD	No	PR
PR	CR Non-CR/Non-PD	No	PR

Target Lesions & Target Lymph Nodes	Non-Target Lesions & Non-Target Lymph Nodes	New Sites of Disease	Overall Objective Status
CR/PR	Not All Evaluated*	No	PR**
SD	CR Non-CR/Non-PD Not All Evaluated*	No	SD
Not all Evaluated	CR Non-CR/Non-PD Not All Evaluated*	No	Not Evaluated (NE)
PD	Unequivocal PD CR Non-CR/Non-PD Not All Evaluated*	Yes or No	PD
CR/PR/SD/PD/Not all Evaluated	Unequivocal PD	Yes or No	PD
CR/PR/SD/PD/Not all Evaluated	CR Non-CR/Non-PD Not All Evaluated*	Yes	PD

*See Section 11.431

** NOTE: This study uses the protocol RECIST v1.1 template dated 2/16/2011. For data collection and analysis purposes the objective status changed from SD to PR in the MCCC protocol RECIST v1.1 template as of 2/16/2011 and to match RECIST v1.1 requirements.

12.0 Descriptive Factors

- See stratification factors section 5.0

13.0 Treatment/Follow-up Decision at Evaluation of Patient

- 13.1 Patients found ineligible will be replaced, as will cancels.
- 13.2 Patients who are stable will continue treatment per protocol.
- 13.3 Patients who develop PD while receiving therapy or once in observation will go to the event-monitoring phase.
- 13.4 Patients who go off protocol treatment for reasons other than PD will go to the event-monitoring phase per Section 18.0.
- 13.5 Observation/Event Monitoring: If the patient has completed therapy and remained stable, the patient will be observed every 3 months (+/- 1 month) for 3 years (observation phase) post RT. Then, every 6 months (+/- 3 months) (event monitoring) for an additional 2 years. For a total of 5 years observation/event monitoring from time of registration
- 13.6 If a patient fails to complete the entire course of treatment for reasons other than toxicity or PD, the patient will be regarded as inevaluable and will be replaced.
- 13.7 A patient is deemed *ineligible* if after registration, it is determined that at the time of registration, the patient did not satisfy each and every eligibility criteria for study entry. The patient may continue treatment off-protocol at the discretion of the physician as long as there are no safety concerns, and the patient was properly registered. The patient will go directly to the event-monitoring phase of the study (or off study, if applicable).
 - If the patient received treatment, all data up until the point of confirmation of ineligibility must be submitted. Event monitoring will be required per Section 18.0 of the protocol.
 - If the patient never received treatment, on-study material must be submitted. Event

monitoring will be required per Section 18.0 of the protocol.

13.8 A patient is deemed a *major violation*, if protocol requirements regarding treatment in cycle 1 of the initial therapy are severely violated that evaluability for primary end point is questionable, which is to be determined by the Biostatistician and Principal Investigator. All data up until the point of confirmation of a major violation must be submitted. The patient may continue treatment off-protocol at the discretion of the physician as long as there are no safety concerns, and the patient was properly registered. Event monitoring will be required per Section 18.0 of the protocol. If a treatment deviation occurs wherein a patient is administered an alternative standard of care chemotherapy the patient will be followed and data will continue to be collected according to section 4.0.

13.9 A patient is deemed a *cancel* if he/she is removed from the study for any reason before any study treatment is given. On-study material and the End of Active Treatment/Cancel Notification Form must be submitted. No further data submission is necessary.

14.0 Body Fluid Biospecimens

None

15.0 Drug Information

Radiation will be accompanied by concurrent standard platinum doublet chemotherapy under the direction of the treating medical oncologist.

Based on this flexible "pick the winner" design, if both arms have a PFS rate at 1-year of 48%, then each arm has a 44% probability of being picked the winner based on PFS rate at 1-year and the probability that the trial is statistically ambiguous and selection of a winning arm will be allowed to include other factors in addition to the PFS rate at 1-year is 12%.

If one arm has true PFS rate of 53% and 1 arm has a true PFS rate of 63%, then the arm with 53% PFS rates has a 21% chance of being picked the winner based on PFS rate at 1-year; the arm with the 63% PFS rate has a 69% chance of being picked the winner based on PFS rate at 1-year alone; and the probability that the trial is statistically ambiguous is 10%.

Properties of the proposed "pick the winner" design were computed using the "pselect" function within the "clinfun" package in R.

No interim analyses will be conducted for PFS.

16.211 Over Accrual: If more than the target number of patients are accrued, the additional patients will not be used to evaluate the stopping rule or used in any decision making process. Analyses involving over accrued patients are discussed in Section 16.313.

16.22 Sample Size: As of May 16, 2018 7 patients ($n_A=3$, $n_B = 2$, $n_C=2$) have been enrolled in 3 cohorts onto this trial. As of Amendment 3 we remove the 66 Gy (Arm B) dose level, and amend the necessary sample size. In order to sufficiently power this amended protocol, 42 total ($n=21$ per arm) evaluable patients will need to be accrued onto this randomized phase II study unless undue adverse events are encountered. We anticipate accruing an additional 6 patients (3 per dose level) to account for ineligibility, cancellation, major treatment violation, or other reasons. Maximum projected accrual is therefore 48 patients total (including the five patients enrolled prior to Amendment 3). Therefore, we will need to accrue 43 additional patients from the time of Amendment 3. The inclusion of the two patients enrolled into the previously open arm (66 Gy) dictates that a total of 50 patients will be accrued for the duration of this trial.

16.23 Accrual Time and Study Duration: The anticipated accrual rate is approximately 2 patients per month based on physician estimate. Therefore, the accrual period for this randomized phase II study is expected to be 24 months. The final analysis can begin approximately 36 months after the trial begins, i.e., as soon as the last patient has been observed for 12 months.

16.24 Power and Significance Level: For the primary analysis, it is assumed that the 1-year PFS rate for 60 Gy is 48% whereas the 1-year PFS rates for 72 Gy is 63% (the later based on Chang et al., 2015), . It is also assumed that the distributions of PFS times for

each dose group follow an exponential distribution, and the probability of declaring that evidence exists that PFS is superior for 72 Gy relative to 60 Gy is selected for further studies under various PFS rates is shown in the following table:

N per arm	PFS rate Trt 1	PFS rate Trt 2	Probability of a statistically ambiguous result*	Probability of selecting Trt 1†	Probability of selecting Trt 2†
21	0.48	0.48	0.12	0.44	0.44
21	0.48	0.53	0.12	0.31	0.57
21	0.48	0.63	0.08	0.12	0.80
21	0.53	0.63	0.10	0.21	0.69

*See section 16.21

† Selection based on PFS rate at 1-year alone.

16.25 Other Considerations: Adverse events, quality/duration of response, and patterns of treatment failure observed in this study, as well as scientific discoveries or changes in standard care will be taken into account in any decision to terminate the study.

16.3 Analysis Plan: The analysis for this trial will commence at planned time points (see 16.2) and at the time the patients have become evaluable for the primary endpoint. Such a decision will be made by the Statistician and Study Chair in accordance with CCS Standard Operating Procedures, availability of data for secondary endpoints (e.g., laboratory correlates), and the level of data maturity. It is anticipated that the earliest date in which the results will be made available via manuscript, abstract, or presentation format is 3 years after the trial commences.

16.31 Primary Endpoint

16.311 Definition: The primary endpoint of this trial is PFS. PFS time is defined as the time from randomization to the earliest date of documentation of disease progression or death due to any cause. If a patient dies without a documentation of disease progression the patient will be censored on the last date the disease was evaluated. In the case of a patient starting treatment and then never returning for any evaluations, the patient will be censored for progression on day 1 post-randomization. Progression events will be reviewed and confirmed by a central review panel and the primary analysis will be based on these central reads. A patient will be considered censored at the last follow-up date if progression or death had not been observed at that time.

16.312 Estimation: A Cox proportional hazards model stratified by stratification factors (see Section 5.0) will be used to model PFS as a function of dose to test for an overall dose effect (a one-sided p-value <0.10 will be considered as significant evidence of a dose effect). Subsequently, descriptive statistics and separate Cox models stratified by stratification factors (see Section 5.0) will compare PFS between 72 Gy and 60 Gy (for each, a one-sided p-value <0.10 will be considered as significant evidence of superiority). Kaplan-Meier estimates and curves by dose level will also be generated.

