3.2 Exclusion Criteria

3.21 Any of the following because this study involves an agent that has known genotoxic, mutagenic and teratogenic effects:

- Pregnant women
- Nursing women
- Men or women of childbearing potential who are unwilling to employ adequate contraception

- 3.22 Co-morbid systemic illnesses or other severe concurrent disease which, in the judgment of the investigator, would make the patient inappropriate for entry into this study or interfere significantly with the proper assessment of safety and toxicity of the prescribed regimens.
- 3.23 Weight loss of >10% in the past 3 months
- 3.24 Distant metastases (M1 disease)
- 3.25 Uncontrolled intercurrent illness including, but not limited to, ongoing or active infection, symptomatic congestive heart failure, lupus, unstable angina pectoris, cardiac arrhythmia, or psychiatric illness/social situations that would limit compliance with study requirements.
- 3.26 Receiving any investigational agent, that would be considered as a treatment for the primary neoplasm.
- 3.27 Active second malignancy.
- 3.28 History of myocardial infarction \leq 6 months, or congestive heart failure requiring use of ongoing maintenance therapy for life-threatening ventricular arrhythmias.
- 3.29 Received Chemotherapy for lung cancer within 6 months of registration.
- 3.30 Previous chest radiotherapy that would overlap with the proton field.

4.0 Test Schedule (these are all considered standard of care and are not experimental)

Tests and procedures	Active Monitoring Phase			
	≤30 days prior to registration	During course of RT (every 7 days +/- 2 days)	Observation Every 3 months (+/- 1 month) for 3 years post RT ⁷	Event Monitoring Every 6 months (+/- 3 months) For a total of 5 years post-registration ⁷
History and exam, Wt, ECOG PS	X	X	X	X
Adverse event assessment	X	X	X	X
Height	X			
Pregnancy test ¹	X			
Tumor measurement ²	X		X	X
Pulm function tests DLCO, FEV1	X ⁴		X ⁶	
CT (chest preferably with contrast)	X		X	X
MRI, or CT of head	X			
PET /CT	X			
LASA/ QOL (appendix II)	X		X	
CBC/Chemistry panel ³	X	X	X	
Histologic confirmation of NSCLC ⁵	X			

1. For women of childbearing potential only. Must be done ≤7 days prior to registration.
2. Refer to section 11.0 for lesion evaluation and response

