3. Glucose, Calcium, Albumin, Total Protein, Sodium, Potassium, CO2 (carbon dioxide, bicarbonate), Chloride, BUN (blood urea nitrogen), Creatinine, ALP (alkaline phosphatase), ALT (alanine amino transferase), AST (aspartate amino transferase), Bilirubin; chemistry and CBC will be monitored during chemotherapy per medical oncology standards
4. PFT's can be up to 90 days prior to registration
5. The biopsy can be older than 30 days but must be done no more than 90 days prior to registration)
6. To be completed at 1 year post only
7. If participant is unable to return to research site then study staff will attempt to obtain outside records

5.0 Stratification Factors:

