11.0 Treatment Evaluation

NOTE: This study uses protocol RECIST v1.1 template dated 2/16/2011. See the footnote for the table regarding measurable disease in Section 11.44, as it pertains to data collection and analysis.

Response and progression will be evaluated in this study using the new international criteria proposed by the revised Response Evaluation Criteria in Solid Tumors (RECIST) guidelines (version 1.1)¹³ Changes in the largest diameter (unidimensional measurement) of the tumor lesions and the short axis measurements in the case of lymph nodes are used in the RECIST guideline.

11.1 Schedule of Evaluations: For the purposes of this study, patients should be reevaluated every 12-16 weeks during the active phase.

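### Section 16.311 censors living, progression-free patients at an undefined last follow-up date rather than the last tumour evaluation, so the 1-year PFS rate can be inflated wherever contact outlasts scanning

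*Combined protocol and SAP*

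**What the plan says.** Section 16.311 defines the endpoint: "PFS time is defined as the time from randomization to the earliest date of documentation of disease progression or death due to any cause". It then uses three different censoring dates.

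- Deaths without documented progression: "the patient will be censored on the last date the disease was evaluated".
- Patients who start treatment and never return for evaluation: "the patient will be censored for progression on day 1 post-randomization".
- Patients alive without progression: "A patient will be considered censored at the last follow-up date if progression or death had not been observed at that time".

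Section 16.11 repeats the first two rules and has none for living patients. The term for the third date is not defined anywhere.

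Progression is assessed by RECIST 1.1 (Section 11.0), and Section 16.311 bases the primary analysis on central reads. Section 11.1 sets the interval: "patients should be reevaluated every 12-16 weeks during the active phase". The Section 4.0 schedule marks chest CT and tumour measurement at every observation and event-monitoring visit after radiotherapy. Footnote 7 to that schedule adds: "If participant is unable to return to research site then study staff will attempt to obtain outside records". It does not say whether those records must include imaging. Under Section 13.4, patients who leave treatment for reasons other than progression go to event monitoring, where visits and scans are every 6 months (+/- 3 months). I found no rule for missed scans and no PFS sensitivity analysis.

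**The concern.** A patient known to be alive is not thereby known to be progression-free. Take a patient whose last CT was at month 4 and who is known alive at month 13. Read literally, 16.311 keeps this patient in the risk set as progression-free through 1 year, although nothing was observed about the tumour after month 4. Had the same patient never been scanned, the day-1 rule would credit no progression-free time at all. The other two rules treat the evaluation as the limit of what is known, and this one does not.

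Section 16.21 picks the winner on the observed 1-year PFS rate, with 21 patients per arm and a 15-point margin. The same censoring dates feed the Cox model and the Kaplan-Meier curves in 16.312. If contact outlasts scanning more often in one arm, that arm's rate rises for a reason unrelated to dose.

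**Working it through.** **1. The plan's own figures.** Treating the arms as two independent Binomial(21, p) counts, with only exact ties ambiguous, reproduces the Section 16.24 table. For 0.48 v 0.63 it gives 0.076 / 0.126 / 0.798 (ambiguous / select the lower-rate arm / select the higher-rate arm), against the stated 0.08 / 0.12 / 0.80. The calculation has no censoring input, so this point changes no stated design figure.

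**2. Inputs.** From the documents: exponential PFS, 1-year rates of 48% and 63%, 21 per arm, at least 12 months of follow-up (16.11, 16.21, 16.24). Assumed, because the documents are silent: a share f of patients stops being scanned in year 1 but stays in contact past month 12. No deaths without progression are modelled. S(t) is PFS at month t.

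**3. One patient, last scanned progression-free at month 4.** Last-follow-up censoring credits this patient fully at month 12. Censoring at the scan credits, in expectation, S(12)/S(4) = S(12)^(8/12). The effect on an arm of 21 is (1 - S(12)^(2/3))/21.

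- At 48%: 0.48^(2/3) = 0.613; 0.387/21 = 1.8 points.
- At 63%: 0.63^(2/3) = 0.735; 0.265/21 = 1.3 points.

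**4. A share f, last scan uniform over months 2 to 10, progression otherwise seen when it occurs.** The large-sample estimate under 16.311 is (1 - f) S(12) + f m, where m is the mean of S(u) over u from 2 to 10. With hazard h = -ln S(12)/12, m = [S(2) - S(10)]/(8h), which is 0.700 at 48% and 0.797 at 63%.

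| True rate | f = 10% | f = 20% |
|---|---|---|
| 48% | 0.9 x 0.48 + 0.1 x 0.700 = 50.2% | 0.8 x 0.48 + 0.2 x 0.700 = 52.4% |
| 63% | 0.9 x 0.63 + 0.1 x 0.797 = 64.7% | 0.8 x 0.63 + 0.2 x 0.797 = 66.3% |

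The shift is about 2 points at 10% and 3 to 4 points at 20%.

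**5. Scheduled scans.** Suppose radiotherapy lasts about 1.4 months (assumed), scans fall at 4.4, 7.4 and 10.4 months, and stoppers have 0, 1 or 2 scans with equal chance. Simulation of 60,000 patients per setting gives these 12-month Kaplan-Meier values:

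| True rate | f | Last follow-up | Last evaluation | Shift (points) |
|---|---|---|---|---|
| 48% | 0 | 0.529 | 0.529 | 0 |
| 48% | 10% | 0.556 | 0.530 | 2.6 |
| 48% | 20% | 0.584 | 0.530 | 5.4 |
| 63% | 0 | 0.670 | 0.670 | 0 |
| 63% | 10% | 0.689 | 0.670 | 1.9 |
| 63% | 20% | 0.711 | 0.671 | 4.0 |

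Two variants are smaller. If only the 10.4-month and later scans are missed, the shift is about 1 point at 10% and about 2 points at 20%. If the day-1 rule is applied to the never-scanned third of stoppers, the estimate is [(1 - f) S(10.4) + (f/3)(S(4.4) + S(7.4))]/(1 - f/3). At 48% the inputs are 0.529, 0.764 and 0.636, giving 0.541 at 10% and 0.554 at 20%, shifts of 1.2 and 2.5 points from 0.529.

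**6. Effect on selection.** Suppose both true rates are 48% and one arm alone reads 5 points high (0.53). That arm's chance of selection rises from 0.44 to 0.57 under the one-response margin that reproduces the plan's table. Under the written 15-point margin (0.15 x 21 = 3.15, so at least 4 patients) it rises from 0.14 to 0.23.

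**The case against.** The strongest reply is that the two dates should usually coincide. CT and tumour measurement are due at every post-radiotherapy visit, eligibility criterion 3.19 requires willingness to return for at least 1 year, and Section 7.4 requires return every 3 months during observation. The protocol also uses follow-up for tumour assessment (11.33), and the day-1 rule suggests no intention to credit unevaluated patients. Outside records may contain scans. All of this stands. It limits how often the problem arises, but nothing in it makes the last evaluation the censoring date.

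A reader might infer four stronger things that the documents do not support.

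- That the 1-year rate is inflated. With complete scanning the bias is zero, and no missed-scan rate is given.
- That one patient is worth 1/21 = 4.8 points. That compares crediting the patient with counting a progression; censoring is the relevant alternative, which gives 1.3 to 1.8 points.
- That censoring at the last scan recovers 48% and 63%. That needs progression to be seen continuously and scan-stopping to be unrelated to prognosis. With scheduled scans, both rules read 53% and 67% even with nothing missed, because the 12-month estimate reflects the 10.4-month scan. If patients who will progress within the year are three times as likely to stop scanning (assumed), last-scan censoring still gives about 50% for a true 48% at 10% unscanned.
- That one arm will gain. Selection compares arms, similar gaps largely cancel, and nothing in the documents shows that gaps will differ by dose.

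**Conclusion.** The point holds as a conditional one. Section 16.311 leaves the censoring date for living patients undefined and not tied to tumour evaluation, at odds with the other two rules in the same paragraph, and no other section corrects it. Any resulting bias in 1-year PFS is upward.

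Its size rests on an assumed missed-scan rate: about 2 to 5 points if 10% to 20% of patients stop scanning early or late in year 1 while staying in contact. It is about 1 to 2.5 points if only late scans are missed or the day-1 rule takes precedence for never-scanned patients, and zero if scanning is complete. The threat to the choice of arm depends on the gaps being unequal. The sentence should be changed because the correction is cheap and the rule is ambiguous as written. This is not evidence that the trial's result will be wrong.

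**What to change.** Replace the sentence in Section 16.311 with: *A patient alive without documented progression is censored at the date of the last adequate disease evaluation showing no progression (day 1 if never evaluated).* Put the same rule in Section 16.11, which has none for living patients. Keep the last follow-up date for overall survival, define it there, and report PFS with last-follow-up censoring as a sensitivity analysis. Tabulating by arm the gap between last evaluation and last contact would show whether the gaps differ.

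The cost is a small text change and one extra analysis. Tumour evaluations are already scheduled, so no new procedures are needed. PFS follow-up becomes slightly shorter for a few patients, and the change reduces but does not remove bias if missed scans are related to prognosis.
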